4.4.2. Missed dose instruction for donepezil

- In accordance with SmPC.

4.4.3. Study Partner Role in Compliance

Due to the varying dosing schedules during titration, study partners are asked to support participant compliance by:

- Reminding participants of scheduled doses.
- Monitoring and reporting any side effects.
- Assisting in documenting any missed or delayed doses in the subject diary.

The study partner will be instructed by the study personnel at site on how to support the participant in completing the subject diary and how they can be supportive in terms of compliance.

4.4.4. Dose escalation:

Based on tolerability, including adverse events and laboratory testing, the study clinician will decide whether the dose will be escalated as per the study plan. If clinical tolerability is deemed acceptable, the participant will receive the next dose level. If not the previous dosing regime will be continued. The detailed handling of this situation is outlined in a dedicated SOP.

4.5. End-of-Study Definition

The end of the study is defined as the date of the last visit of the last participant in the study. The date for the end of study is set to 31 December 2025. However, the date for the research active period is set to 01 January 2028. All analyses within the scope of this study will be completed by the 01 January 2028.

A participant is considered to have completed the study if the participant has completed all periods of the study including the safety follow-up visit 1-week after the last dose (table 1). Safety follow-up visit conducted within 28 days after the final dose of phenserine at the 8 week visit is considered sufficient since bioavailability when administered orally has a half-life for AChE plasma inhibition was 8.25 hr (26).

4.6. Early Termination of the Study

Reasons for early termination of the clinical trial may include:

- Ethical concerns,
- insufficient recruitment of participants,
- early evidence of benefit or harm of the investigational medicinal product,
- patient safety appears to be at risk,
- the sponsor deems it necessary to terminate the study for safety reasons,
- the study proves to be not feasible.

The sponsor shall discuss the decision to terminate the study with the steering committee. The study may be terminated at individual sites if GCP requirements are not met or if the respective sites are not working in accordance with GCP guidelines.

5. Study Population

5.1. Inclusion Criteria

1. A diagnosis of AD based on the most recent NIA-AA diagnostic criteria for AD (27).
2. A significant change on a validated AD amyloid or tau biomarker (as determined either by visual reading of amyloid PET scans [using any of the approved ligands], or CSF A β 1-42 or blood p-tau 217 levels [cut-off as determined by the individual laboratory]).
3. MCI (FDA stage 3) or mild dementia (FDA stage 4) based on a CDR Global rating of 0.5 (MCI) or 1.0 (mild dementia) (28)
4. An MRI scan within the past two years that has no findings inconsistent with AD.
5. Participants who have recently participated in other clinical trials or have been under treatment with memantine or acetylcholinesterase inhibitors (e.g., Donepezil, Rivastigmine, Galantamine) must undergo a washout period of at least 4 weeks prior to the start of the study.
6. Capacity to give informed consent based on the clinical judgement of an experienced clinician.
7. The participant has an individual who is in regular, daily contact via phone or in-person visits and who can act as a reliable study partner and provide meaningful input into rating scales.
8. Age \geq 50 years.
9. Fluency in Norwegian and evidence of adequate premorbid intellectual functioning.
10. Capable of participating in all scheduled evaluations and complete all required tests.
11. Females of childbearing potential and males must commit to use highly effective methods of birth control (see highly effective birth control for male and females described in 11.4 appendix 4) from signing informed consent form until at least 30 days after last administration of phenserine or donepezil.

5.2. Exclusion Criteria

1. Significant cerebrovascular disease, as indicated by clinical history, neurological examination, or on MRI (including cortical infarction or deep white matter or periventricular white matter hyperintensities with a Fazekas scale score of 3 (29).
2. Current treatment with a cholinesterase inhibitor or memantine.
3. Hypersensitivity to AChE inhibitors or related compounds: Known hypersensitivity to donepezil, piperidine derivatives, or any formulation components.
4. Participants undergoing or planning procedures requiring anesthesia with depolarizing neuromuscular blockers (e.g., succinylcholine) due to the risk of prolonged paralysis or apnea when combined with AChE inhibitors.
5. Active peptic ulcer disease or gastrointestinal bleeding, or a history of gastrointestinal ulcers or bleeding.
6. Severe cardiac conditions: Significant arrhythmias, sick sinus syndrome, supraventricular conduction abnormalities, or other cardiac rhythm disorders that could pose a risk with cholinesterase inhibitors.

7. Severe respiratory disease: Chronic obstructive pulmonary disease (COPD) or poorly controlled asthma.
8. History of urinary obstruction or bladder issues, particularly those requiring catheterization.
9. Current clinically significant depression or other mental disorders likely to affect cognition or interfere with study participation.
10. Participants using sedating drugs, if unavoidable, will be excluded from the study. However, short-acting sleep medications can be used if taken as recommended and if the participant has maintained a stable regimen for at least 3 months prior to the start of the study.
11. Current participation in any other drug trial(s).
12. Currently ongoing life-threatening disease, such as metastatic cancer, advanced cardiovascular disease, advanced respiratory disease, terminal kidney disease, or advanced stages of an infectious disease.
13. Any current or past neurological disease unrelated to AD and with cognitive sequelae.

5.3. Lifestyle Considerations

- No lifestyle/dietary restrictions are required.

5.4. Screen Failures

A screen failure occurs when a participant who has consented to participate in the clinical study is not subsequently assigned to study intervention/entered in the study. A minimal set of screen failure information is required to ensure transparent reporting of screen failure participants to meet the CONSORT publishing requirements and to respond to queries from regulatory authorities. Minimal information includes demography, screen failure details, eligibility criteria, and any SAE. Depending on the cause of screen failure, the Centre PI will determine whether re-screening is allowed. For example, if there is prohibited drug treatment, changes in the drug regimen can be made, providing considered safe by treating physician and study physician.

5.5. Criteria for Temporarily Delaying

The study procedures will be temporarily delayed if there is emerging new evidence concerning the safety of phenserine.

6. Study Intervention(s) and Concomitant Therapy

6.1. Study Intervention(s) Administered

In this study, phenserine will be formulated as a capsule, with dosages 5mg and 10mg. Participants randomized to the phenserine arm will start at 5 mg twice daily (bd) with escalations every two weeks, as tolerated until a maximum dose of 10 mg three times daily (tds).

Participants randomized to the donepezil arm will start at 5 mg tablet once daily (od) with escalation, to 10 mg od from Week 5, as tolerated.

6.1.1. Table 3. Study Intervention(s) Administered

Intervention Name	Phenserine tartrate	Phenserine tartrate	Phenserine tartrate	Donepezil	Donepezil
Intervention Description	First two weeks,	W3-W4	W5-W8	First four weeks	W5-W8
Type	drug	drug	drug	drug	drug
Dose Formulation	capsule	capsule	capsule	tablet	tablet
Unit Dose Strength(s)	5 mg	10 mg	10 mg	5 mg	10 mg
Dosage Level(s)	5 mg bd	10 mg bd	10 mg tds	5 mg od	10 mg od
Route of Administration	oral	oral	oral	oral	oral
Use	intervention	intervention	intervention	Comparator	Comparator
IMP and NIMP/AxMP.	IMP	IMP	IMP	IMP	IMP
Sourcing	Provided centrally by the sponsor	Provided centrally by the sponsor	Provided centrally by the sponsor	Provided centrally by the sponsor	Provided centrally by the sponsor
Packaging and Labeling	KRAGTA B	KRAGTAB	KRAGTAB	Local Pharmacy*	Local pharmacy*

*Donepezil will be purchased commercially, eg with standard labelling, and stored locally at pharmacy or study centre.

6.1.2. Table 4. Study Arm(s)

Arm Title	Start dose	Maintenance dose	Donepezil	Maintenance of Donepezil
Arm Type	intervention	Intervention	Comparator	Comparator
Arm Description	Participants will receive 5mg mg bd on Week 1-2	Participants will receive 10 mg bd from Week 3-4 10 mg TDS from Week 5-8	Participants will receive 5mg od from week 1-4	Participants will 10mg od from week 5

6.2. Preparation, Handling, Storage, and Accountability

Preparation, handling, and storage of the IMP have been described in detail in the IB. In summary, the phenserine tartrate capsules manufactured under Good Manufacturing Practice (GMP) conditions. Each capsule contains 5 mg, 10mg and of phenserine tartrate, formulated with excipients to ensure stability and bioavailability.

The substance donepezil (under the brand name Aricept®) is a resale product. No additional manufacturing or labeling measures is necessary for this study.

The IMP, donepezil will be available in 5 mg and 10 mg strengths (table 3) and will be obtained from the study personnel at the local pharmacy by prescription. Please refer to section 11.8 (Appendix 8) for detailed information on prescription procedure for dispensing donepezil. We have based the use of donepezil as a treatment in the study on the original product from Pfizer, but it is also possible to use generic products of donepezil if this is what the local pharmacy has for dispensing. Participants randomized to treatment with donepezil will follow the treatment plan according to the patient information leaflet. These tablets are approved for clinical use and comply with all relevant safety and efficacy standards. Also participants allocated to treatment with donepezil will be asked to fill a subject diary for drug compliance. The subject diary template is available in appendix 7 below.

Capsules and tablets should be handled with care to avoid exposure to moisture or excessive heat. Personnel handling the medicines must follow standard safety procedures, including wearing gloves and protective clothing if necessary.

All capsules and tablets must be accounted for using a drug accountability log. Each site is responsible for tracking the receipt, dispensing, and return of capsules/tablets, ensuring accurate records are maintained for compliance with regulatory requirements.

6.3. Assignment to Study Intervention

In this study, participants will be randomized 6:2 to phenserine or donepezil in an open-label manner. Drug Dispensing and Dosing Instructions

Randomized subjects will be dispensed a single bottle of phenserine or donepezil drug product on Day 0 following all baseline assessments and confirmation of eligibility. Each participant will take the first dose in clinic and be instructed on how to continue dosing at home through the next two weeks (5 mg bd for the phenserine group and 5 mg od for the donepezil group). As shown in Figure 1, at the end-of-Week 2 visit, participants will undergo safety and tolerability assessments, and will be tested to determine their cholinesterase inhibition level. Based on tolerability, participants in the phenserine treatment group may be titrated to the next higher dose level (10 mg bd) for the next two weeks of treatment, while participants in the donepezil arm will continue the 5 mg od regimen. Adequate supplies will continue to be provided to the participants at this visit and in future visits to ensure they have adequate study drug (with an appropriate overage) to ensure that there are no disruptions in their daily dosing regimen through to the next study visit. At the end-of-Week 4 visit, and based on safety/tolerability assessments, participants in the phenserine arm may be escalated to 10 mg tds through to the end-of-Week 8 visit and participants in the donepezil arm may escalate to 10 mg od and remain at that dose through the remainder of the study (i.e., end of Week 8, as long as it is tolerated. Participants in both arms will return for follow-up assessments at the end-of-Week 6.. At the end-of-Week 8 visit, all participants will undergo final on-drug study assessments and will then return to the site for a final safety follow-up visit within 1 week of the last study-drug dose.

6.3.1. Allocation- procedure to randomize a participant

Both the subjects and the site staff will know which treatment they are assigned. Participants and site staff, will be blinded to the results of the exosomal and blood/CSF biomarker evaluations until the study is completed.

Participants will be identified by a unique study ID. Personal identifiable data (such as name, address, and other contact details) will be collected, but will be stored separately from the research data and will be destroyed as per applicable regulations when the project is concluded. Data will be managed by the University Hospital Stavanger clinical trials unit, following all relevant data protection guidelines and all relevant Clinical Trial Regulations. Data will be collected and stored electronically in accordance with the Data Protection Act 2018 and ICH GCP E6 R2. Data will be cleaned and validated appropriately, with a full Data Protection Impact Assessment (DPIA) undertaken along with development of a comprehensive Data management Plan (DMP) before the first participant is recruited.

[figure not shown]
The computer-generated randomized allocation sequence will be produced by an independent, unblinded statistician and imported into the Viedoc Electronic Data Management System (EDCS). The unblinded statistician will generate randomisation lists using using R v4.2 as implemented in <https://icostatistics.shinyapps.io/randlist/> Participants will be screened for eligibility and first included by study physicians after informed consent. After study inclusion the participant will be randomized via Viedoc. The participant will be allocated treatment arm via Viedoc and receive the assigned IMP treatment at the first baseline visit by a study nurse. The study nurse will record the date of IMP distribution and the time and date of the first dose administered in Viedoc.

6.3.2. Subject identification

Patients who meet the inclusion criteria will be identified by a study investigator and will receive a brief information letter about the study. They will be explicitly informed that participation is entirely voluntary and that their decision, whether to participate or not, will not adversely affect their care at the hospital.

Participants will be identified by a unique study ID. Personal identifiable data will be stored separately to research data, with only a small select group of key research staff having access, and will be destroyed as per applicable regulations when the project is concluded. Other study staff will only have access to de-identified data. Data will be managed by the University Hospital Stavanger research unit, following all relevant data protection guidelines and all relevant Clinical Trial Regulations. Data will be collected and stored electronically in accordance with the Data Protection Act 2018 and ICH GCP E6 R2. Data will be cleaned and validated appropriately, with a full Data Protection Impact Assessment (DPIA) undertaken along with development of a comprehensive Data management Plan (DMP) before the first participant is recruited. Data collection for this study will be conducted through an Electronic Data Capture (EDC) system known as Viedoc, which is further detailed in Appendix 5.

The informed consent forms will clearly convey to the participants that they have the right to withdraw from the study at any point without any negative impact on their care or treatment. The primary analysis will be based on the modified intention-to-treat population. Participants will be analyzed according to their allocated treatment group irrespective of what treatment they received. Patient throughput for the final analysis will be illustrated using a CONSORT flow diagram (Figure 3).

Figure 3. CONSORT CHART

6.4. Blinding

The study intervention will be open label. No blinding will be performed. Participants and site staff will, however, will be blinded to the results of the exosome and blood/CSF biomarker evaluations until the study is completed.

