To evaluate compliance, the study will measure the extent to which participants take the study medication according to the protocol. Compliance will be assessed using the subject diary and the registration of returned capsules.

Exploratory Objectives:

To evaluate changes in specific biomarkers of Alzheimer's Disease (AD) in cerebrospinal fluid (CSF): A β 1-40, A β 1-42, Tau, and p-tau, and in blood plasma: p-tau217 and NfL.

To assess phenserine's potential short-term effects on specific cognitive tests using the FLAME Memory Composite and other cognitive sub-tests.

To evaluate changes in overall cognitive function using the Montreal Cognitive Assessment (MoCA):

Primary Endpoint:

Changes in exosome biomarkers of pre-programmed cell death, synaptic integrity and function, neuroinflammation, and AD-related protein trafficking in participants treated with phenserine versus those treated with donepezil. Although patients and site staff will be unblinded to the treatment modality administered, they will be blinded to the results of the biomarker evaluations until the study is completed.

Key Secondary Endpoints:

Safety and tolerability of phenserine compared to donepezil in participants with early or mild AD based on the frequencies of reported or observed adverse events (AEs) and serious adverse events (SAE), vital signs, clinical laboratory evaluations, ECGs, and modified CSSRS scores.

Other Secondary Endpoints:

Pharmacokinetic parameters will be assessed at steady state for determination of dose-response relationships for phenserine and donepezil.

Evaluate the proportion of participants in the phenserine arm who achieve the target AChE inhibition of approximately 45%, stratified by dose regime and assess the time required to reach the target AChE inhibition of ~45% and the duration participants maintain this inhibition during the treatment period. Blood samples will be analyzed for Acetylcholinesterase (AChE) activity using a modified Micro-Ellman method (22) normalized to recombinant AChE enzyme activity (refer to Appendix 10).

Compliance will be recorded, based on drug count and subject diary, including the proportion of participants complying with the treatment schedule. Compliance is defined as drug intake within 80-120% of the scheduled dosing.

Exploratory Endpoints:

Assess changes in Alzheimer's Disease (AD) biomarkers in cerebrospinal fluid (CSF): A β 1-40, A β 1-42, Tau, and p-tau, and in blood plasma: p-tau217 and NfL.

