3.2. Outcome Measures

3.2.1. Primary Outcome Measure

The primary outcome measure will assess changes in four panels of exosome biomarkers, including markers of pre-programmed cell death, synaptic integrity and function, neuroinflammation, and AD-related protein trafficking in participants treated with phenserine versus those treated with donepezil. Panel details are presented in separate standardized operationalized procedures (SOPs).

Although participants and site staff will be unblinded to the treatment modality administered, they will be blinded to the results of the exosome and blood/CSF biomarker evaluations until the study is completed.

The pre-programmed cell death panel (PNCDD) will investigate key factors such as BAX, Bcl-2, which will provide insights into preprogrammed cell death processes (4,17) and any changes in the profile observed following treatment with phenserine or donepezil. The second panel focuses on synaptic markers, including synaptotagmin, offering a nuanced understanding of synaptic integrity and function. The third panel is centered on evaluating inflammatory biomarkers, including TNF- α , IL-1 β , IL-6, and IL10, and the fourth panel will evaluate AD-specific markers, including A β 1-42, and will elucidate key molecular signatures associated with AD pathology. This comprehensive evaluation of mechanistic biomarkers through exosome technologies aims to deliver a detailed understanding of the impact of phenserine versus donepezil on various facets of AD neuropathology, contributing to the trial's primary objective.

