10.3. Statistical Analyses

All primary, secondary and exploratory outcomes will be collected for all participants, except that PK analyses will be performed only for participants randomized to phenserine.

Trial management and data management will be conducted by the University Hospital Stavanger Clinical Trials Unit and the trial statistics will be led by [name], King's College London.

Standard safety data (including all AEs, TEAEs, SAEs, important clinical laboratory findings, and AE-related discontinuations) will be summarized for each treatment arm and dose level.

Exosome biomarker values will be natural log transformed to avoid skewness. To assess the effect of phenserine on a given biomarker, a linear mixed-effects model will be used, with treatment groups (phenserine vs donepezil), time, baseline biomarker, and plate to plate variability in exosome concentration (determined by NanoSight) as fixed effects and participant identification treated as a random effect.

To demonstrate that dropout rates are Missing at Random (MAR), we will calculate the correlation between dropout indicators (e.g., whether a participant drops out) and key covariates, including treatment group, baseline characteristics, and other relevant random effect categories. Based on prior observations (liraglutide trial for example), we expect that the likelihood of dropout will largely be explained by observed factors, especially drug treatment status. A logistic regression model will be used, with the dropout indicator as the dependent variable and treatment status, baseline covariates, and any other relevant factors as independent variables. If the model explains a significant portion of the dropout pattern, this would support the MAR assumption. Sensitivity analyses will also be conducted to assess the robustness of this finding under alternative missingness mechanisms.

For clinical secondary and exploratory outcomes, change from baseline will be calculated at the final study assessment (mean, n, standard deviation, standard error, minimum and maximum scores).

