[name] is the Chief Investigator and will have academic oversight of the trial and be responsible for reporting to the funder. The Coordinating Investigator for the PATH-1 RCT is [name], who will have overall responsibility for the conduct of the trial and interactions with the sponsor, regulator, and ethics committee, as appropriate and required during the course of the trial. [name] will be responsible for the analysis of exosomes, the primary outcome measure.

This trial will be managed by a Trial Management Group (TMG), which will include the Principal Investigators, the Trial Manager and a patient representative. The TMG will be co-chaired by the Chief Investigator and the Coordinating Investigator. The group will meet at three-month intervals and additionally as appropriate. The TMG will have direct oversight of and responsibility for the study. The remit of the TMG will also include overall progress of the trial and to monitor progress against milestones. Any discrepancy from milestones will be highlighted and a plan developed to address any difficulties. The day-to-day management of the trial will be conducted by the Trial Manager, who will report to the Coordinating Investigator on a regular basis. The Trial Manager will send a written report to the chairs of the TMG before each TMG meeting, detailing progress. Any non-urgent major decisions will be made by the TMG.

The Trial Steering Committee (TSC), , will meet twice over the course of the study (with additional meetings convened if requested by the Data and Safety Monitoring Board (DSMB) and will be responsible for oversight of trial governance and reporting to the sponsor.

A DSMB chaired by [name] (Geriatrician) will provide independent review of unblinded safety data collected during the study. All serious adverse events (SAEs) will be reviewed by the chair within 24 hours, and summary trial reports will be reviewed by the full committee every three months through its completion. The data will be prepared for these reviews by a separate team of unblinded data managers and statisticians who have no involvement in the day-to-day conduct of the study.

The committee will be governed by a charter and will make recommendations to stop, continue or modify the trial based on their ongoing review of the safety data. Emergency meetings will be convened on an ad hoc basis and as warranted by emergent study data.

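### Neither document says that the exosome laboratory, or whoever excludes assay errors, is masked to arm and visit, and the SAP model drops the protocol's plate term

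*Protocol*

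**What the plan says.** Protocol Section 6.4 makes the intervention open label and then reads: "No blinding will be performed". It adds that participants and site staff "will be blinded to the results of the exosome and blood/CSF biomarker evaluations until the study is completed". Section 3.2.1 (Primary Outcome Measure) says the same: "Although participants and site staff will be unblinded to the treatment modality administered, they will be blinded to the results of the exosome" and blood/CSF results. The Primary Endpoint text in Section 3, Table 2 and Section 6.3.1 repeat it.

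In Appendix 1 (Section 11.1.1, Trial management) one person "will be responsible for the analysis of exosomes, the primary outcome measure", with no condition on what that person may know. Assay content is placed elsewhere: "Panel details are presented in separate standardized operationalized procedures (SOPs"). Those SOPs are not among the documents.

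On analysis, Protocol Section 10.3 lists "plate to plate variability in exosome concentration (determined by NanoSight") among the fixed effects. SAP Section 7.2 lists treatment, visit and their interaction, with a random intercept per participant and no plate term. SAP Section 5 keeps extreme biomarker values in the primary analysis except those attributed to assay or data collection error. It does not say who makes that attribution, by what criteria, or whether they know the arm.

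**The concern.** Hiding results from people who know the arm is different from hiding the arm from people who produce the results. The plan states the first and is silent on the second. For a laboratory endpoint in an open-label trial, the second is what keeps knowledge of treatment out of the measurement.

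Two routes could connect arm to measured value. One is discretion: a value judged to be an assay error leaves the primary analysis. With four donepezil participants, one exclusion at a visit removes 1/4 = 25% of that arm's data there. The other is layout. The protocol expects plates to differ, and if arms or visits fall unevenly on plates, that difference enters the treatment contrast. The SAP model as listed has no term to absorb it.

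**Working it through.** **1. The plan's own figure.** Inputs from Protocol Sections 10.3 and 10.3.1: difference 2.45 SD, two-sided 0.05, 80% power, 4 per arm. For a two-sample t-test the noncentrality is d / sqrt(1/n1 + 1/n2). At 4 per arm this is 2.45 / sqrt(1/4 + 1/4) = 3.46 on 6 df, giving power 82.1%. At 3 per arm power is 61.9%. The stated 4 per arm reproduces, and nothing below changes it.

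**2. What each stated safeguard covers.**

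| Provision | Covers | Does not cover |
|---|---|---|
| Results withheld from sites and participants (Protocol 6.4) | Site conduct reacting to results | Laboratory knowledge of arm |
| Study ID and de-identified data (Protocol 6.3.1, 6.3.2, 11.1.3) | Personal identity | Allocation; not stated to be withheld |
| SAP final, and deviations classified, before biomarker results are unblinded (SAP 1.1, 3.4.2) | Analysis choices made after seeing results | How samples are handled |
| Extreme values kept by default (SAP 5) | Removal of values merely for being extreme | Masking of the assay-error decision |
| Plate term (Protocol 10.3) | Plate differences in the protocol model | The SAP 7.2 model, which omits it |

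No row masks the laboratory, or the assay-error decision, to arm or visit.

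**3. Size if handling were linked to arm (illustration).** Inputs: 12 v 4 (SAP Section 3), no true effect, a simple t-test on change from baseline with 12 + 4 − 2 = 14 df. The net shift b, in SDs of that change, is assumed; the documents give no value. Noncentrality = b × sqrt(12 × 4 / 16) = 1.732b.

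| Assumed net shift b | Noncentrality | 95% interval excludes zero | Interval covers the true value (zero) |
|---|---|---|---|
| 0 | 0 | 5% | 95% |
| 0.25 SD | 0.433 | 6.9% | 93.1% |
| 0.5 SD | 0.866 | 12.7% | 87.3% |
| 1.0 SD | 1.732 | 36.5% | 63.5% |

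The word *net* matters. If handling adds s to both a participant's baseline and Week 8 values, the change is (Y8 + s) − (Y0 + s) = Y8 − Y0 and the shift vanishes. Only a shift that differs between baseline and later samples, and between arms, survives.

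**4. Plate imbalance (illustration).** Plate capacity and layout are not given. Suppose four plates each hold four participants, filled at random. The four donepezil participants can fall in 16! / (4! × 12!) = 1,820 ways, of which 4 × 4 × 4 × 4 = 256 put one on each plate. The chance that at least one plate has no donepezil participant is 1 − 256/1,820 = 86%. The chance that all four share a plate is 4/1,820 = 0.2%. On these assumptions the likely problem is partial imbalance, not complete confounding.

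**The case against.** A reader might infer from Section 6.4 that the exosome laboratory is unmasked. The documents do not support that. The sentence on blinding directly follows the one on the open-label intervention, and the people named as knowing treatment are participants and site staff. Neither document says the laboratory has the allocation, and coding by study number points mildly the other way. Sample coding, plate layout and repeat rules would normally sit in the SOPs, which are not available here. Exosome re-runs and plate layout are not described in either document, so these remain possible routes, not documented practice.

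A reader might also infer that laboratory masking is the only protection and that none exists. That is too strong: the table above lists several partial safeguards.

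The shifts are assumed, and some would cancel in change from baseline. Even 1.0 SD is 1.0/2.45 = 41% of the effect the sample size assumes. The SAP also plans estimation, not formal testing. That last point gives limited comfort: SAP Section 2.3.2 asks readers to treat the interval as a range of plausible effects, and the coverage column shows how bias damages that reading.

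Finally, masking alone does not prevent arms and plates from coinciding by chance. That stands, and it is why the fix treats layout separately.

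After these points, the silence on masking and the dropped plate term remain.

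**Conclusion.** The concern holds as a gap in the stated plan. Followed as written, the protocol and SAP allow the primary endpoint to be measured, and values excluded, by people who may know arm and visit, under a SAP model without the plate term. Whether this happens cannot be determined without the SOPs, and no bias has been shown.

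The size is illustrative only: about 7%, 13% or 36% of intervals excluding zero instead of 5%, for net shifts of 0.25, 0.5 or 1.0 SD. This rests on an assumed shift that survives the baseline subtraction, 12 v 4 completers, and a simple t-test in place of the mixed model. The change should be made because the endpoint is primary, the comparator arm has four participants, and the remedy is cheap. No sample-size figure changes.

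**What to change.** In Protocol Section 6.4 and the SAP, or by citing the SOP if it already provides this:

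- Send exosome samples to the laboratory under a code that carries neither arm nor visit.
- Keep the laboratory, and whoever releases assay values, masked until the exosome data are locked.
- Decide any re-runs and all assay-error exclusions before codes are opened, and state who decides.
- Have the independent unblinded statistician who already produces the allocation list (Protocol Section 6.3.1) supply a plate map. It should keep each participant's five exosome visits on one plate and spread the donepezil participants across plates as far as numbers allow. A masked laboratory cannot build this map itself.
- Restore the plate term in SAP Section 7.2, or explain its omission there.

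At most 16 × 5 = 80 participant-visit samples are involved. The cost is relabelling, one plate map, and some delay while samples wait until a participant's visits are complete. No extra samples are needed, and open-label conduct at the sites is unchanged.
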